The recently completed Phase 1 of XN at NUNM resulted no statistically significant differences in any mean laboratory values between XN vs. placebo groups at Closeout/Week 8 (all p values>0.10). At Closeout/Week 8, 2 laboratory parameters met halting criteria in Group B, including 1 mild anemia and 1 AST elevation. Notably, all lab abnormalities present at Closeout/Week 8 were resolved upon re-testing. There were no statistically significant differences in the frequency of any laboratory abnormalities between groups, at any timepoint in the trial (pvalues all>0.2). No participants discontinued their study intervention due to AEs. There were no "Grade 3/Severe" or FDA Serious AEs reported in either group. There were no apparent trends in incident AEs in either group over the time course of the trial. Additionally, investigators previously evaluated the effect of 12.5 mg per day of xanthohumol within a formula in adults with IBD, including Crohn's disease. Complete blood count and comprehensive metabolic panel data indicated no adverse changes; mean values were within normal laboratory reference ranges at all time points. All adverse events were non-serious and most were related to preexisting symptoms.¹⁵

There are no known toxicities for human subjects taking oral supplements containing XN. The general population is primarily exposed to XN through consumption of beer. A major brand beer contains about 0.5-1 mg prenylflavonoids (mainly XN and iso-XN) per liter and a bitter microbrew ale may contain as much as 4 mg of total prenylflavonoids.¹⁶ In Europe, a beer/beverage, containing 4 mg of XN per liter, has been on the market for several years without adverse effects having been reported by the consumers. Based on the available human data and the results from the above cited animal studies, we expect that the study participants will not develop adverse effects at the proposed dosage regimens during the 8-week exposure period.

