We aim to extend our preliminary findings related to potential application of XN as a therapeutic by testing its effects in a sample of human adults with CD. We will recruit 32 participants with CD, and randomize them to either 24 mg of XN plus rice protein, or a rice protein placebo for 8 weeks. The study drug will be identical to the preparation used in the Phase 1 trial that preceded this Phase 2 protocol, i.e., XN will be administered as 24 mg of a 99+% pure raw material provided by Hopsteiner USA (NY) combined with 288 mg of rice protein (California Natural Products, Lathrop, CA), 109.3 mg microcrystalline cellulose (Stauber USA, Fullerton, CA), 4.3 mg Aerosil®

Protocol

200 fumed silica (Vivion Inc., San Carlos, CA), and 4.3 mg magnesium stearate (Nitika Pharmaceutical Specialties, Maharashtra, India), and formulated into a capsule by Metagenics, Inc. (Gig Harbor, WA). XN has been combined with a rice protein carrier due to improved bioavailability.⁹

Our *primary working hypothesis* is that XN at the given dose will be safe and tolerable in adults with active CD. We will test this hypothesis by collecting blood samples at screening, baseline, and every two weeks to monitor changes in laboratory values including liver enzymes, renal function markers, and hematological markers. We anticipate very low frequency of treatment discontinuation due to adverse effects.

Our *working hypotheses* of Aims 2, 3, and the Exploratory Aim are that XN and its microbiotaderived metabolites may reduce inflammation and reduce biomarkers of barrier permeability in the inflamed gut. In order to test this hypothesis, we will collect blood, urine, and stool samples at baseline and every two weeks to monitor gut microbiome profiles and measure XN metabolite profiles. We will also measure fecal metabolome (including bile acid profiles) and lipidome profiles, as well as established fecal and plasma indicators of IBD severity, including fecal calprotectin and C-reactive protein. Because the actions of XN and its metabolites target specific abnormalities in CD, we hypothesize that the proposed studies will deliver a mechanism-based biological signature of XN exposure and its effect on CD mitigation.

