Our primary outcome measure for this secondary objective will include fecal calprotectin and circulating levels of inflammatory cytokines as biomarkers of systemic inflammation. The sample size provides >80% power, at a threshold of alpha=0.05, for the detection of a 25% difference in marker changes in response to XN between the healthy adults in the Phase 1 trial and participants in this trial. Additionally, we will measure changes in Crohn's Disease Activity Index (CDAI) score for participants at each clinical visit to first determine eligibility and, second, compare end results to baseline for any change in score. Finally, results will be compared to the previous Phase 1 trial in healthy adults.

Aim 3. Collect samples and measure XN metabolism, gut permeability and impact on the microbiota.

We will assess XN metabolism, gut permeability and impact on the microbiota. Thus, our outcome measures for this objective include microbiota profiles, XN metabolites and bile acid metabolites.

Aim 4. (Exploratory) Generate a computational, theoretical model for assessing and understanding of the interactions between XN and the gut microbiome, and how the identified interactions may mitigate CD.

We will measure biomarkers of gut inflammation and gut integrity, and composition of intestinal microbiome species through various methods including measurement of circulating plasma endotoxin, CD14, intestinal fatty acid-binding protein, lipopolysaccharide-binding protein; lipidomic profiling; and TLR2/TLR4 activation.

8 Trial design

The design will be a triple-masked, randomized, placebo-controlled trial. Upon confirmation of eligibility and documentation of informed consent, those participants still interested and eligible to participate will be randomized to either: XN (24 mg/day plus 288 mg of rice protein plus 117.9 mg of excipients) or placebo (rice protein 288 mg/day plus117.9 mg of excipients) taken by mouth once daily for 8 weeks.

Methods Participants, interventions and outcomes

9 Study Setting

The clinical study will take place at an academic medical center, the National University of Natural Medicine's Helfgott Research Institute in Portland, OR, USA.

10 Eligibility criteria

Crohn's Disease (n=32):

Inclusion criteria

- Adults 21-70 years of age
- Active Crohn's disease not in remission based on a CDAI score >150
- Willing to take isolated Xanthohumol as a dietary supplement for 8 weeks

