- Malignancy within the last 5 years (with the exception of basal cell carcinoma, squamous cell carcinoma, and/or carcinoma in situ of the cervix)
- Women who are lactating, pregnant or planning pregnancy within the next four months
- Typical intake of more than 2 alcohol-containing beverages per day, more than 14 per week, or more than 4 in any single day within the past 14 days.
- Smoking tobacco or use of nicotine products Use of illicit drugs/substances (such as but not limited to cocaine, phencyclidine (PCP), and methamphetamine) within 14 days of screening
- Use of inhaled or ingested *Cannabis* products, including CBD
- Currently participating in another interventional research study, or participated in another interventional research study within 14 days of screening
- Do not have a medical provider available to consult with and/or manage medications for their CD as needed
- Received a vaccination within 14 days prior to clinical screening.

Candidates will be given the option to stabilize or eliminate alcohol intake, allowable dietary supplement and medication intake, exercise, and diet to the requirement stated above for 14 days, and/or eliminate cannabis use and illicit substance and may re-contact the study team after.

11a Interventions

The intervention is XN (24 mg/day plus 288 mg of rice protein plus 117.9 mg of excipients) or placebo (rice protein 288 mg/day plus 117.9 mg of excipients) taken by mouth once daily for 8 weeks.

11b Withdraw/Discontinuation

A participant may elect to withdraw from the trial at any time they choose, if they experience AEs or for no stated reason. However, participants will be actively withdrawn if they demonstrate new onset, moderately severe gastrointestinal AEs, attributable to the intervention. Participants will also be withdrawn if they have any *critical* value return on routine clinical laboratory measures of safety, including changes in blood counts, liver function tests and/or renal function tests.

Safety measures include self-reported adverse events, % new abnormal and mean changes in specified clinical laboratory parameters including red blood cell count, ALT, AST, GGT, bilirubin, alkaline phosphatase eGFR, and BUN: creatinine ratio.

11c Adherence

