Gut integrity and	Plasma concentrations of	ELISA will be used to measure
enterocyte damage	soluble CD14, intestinal	soluble markers of microbial
	fatty acid-binding protein,	translocation from the intestine
	and lipopolysaccharide-	
	binding protein by ELISA	
	Plasma endotoxin by	Plasma endotoxin by Limulus
	Limulus amebocyte lysate	amebocyte lysate assay will measure
	assay	the microbial translocation
	TLR2, TLR4 activation	HEK293 cells pre-transfected with
	by transfected HEK293	TLR4 and TLR2
	reporter cells	
Lipid metabolism	Lipidomics profiling	Liquid chromatography UPLC-QTOF

Primary Outcome: Clinical Safety/Cumulative Toxicology

Standard clinical Complete Blood Counts and toxicology panels including liver and renal function tests will be measured at each bi-weekly clinical visit. Values will be interpreted based on: new abnormal value, change since baseline, new emergency or alert values, and/or the emergence of new diagnostic concerns. All participants' labs will be reviewed by a clinical investigator, and any abnormal lab values meeting halting criteria will be recorded in the database.

Should a participant experience a severe or emergent event: 1. The AE and its severity will be documented; 2. The participant's medical provider will be notified and consulted; and, if unavailable, 3. The DSMB Chair ([name], MD, PhD; Division Chief of General Surgery, OHSU) will be consulted if the study team is unable to reach the participant's physicians.

Secondary Outcome: Fecal Calprotectin

Levels of calprotectin, a marker of CD, will be determined in stool samples using a commercial ELISA kit.

Secondary Outcome: Inflammatory markers

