Exploratory Outcome: Circulating Endotoxin

As an additional measure of gut integrity, levels of lipopolysaccharide (endotoxin), a component of Gram-negative bacteria, will be determined with the Limulus amoebocyte assay. The version of the assay used in this study will be a microplate-based chromogenic, endpoint assay.

Exploratory Outcome: Bacterial Translocation

Bacterial translocation out of the gut lumen will be measured by TLR2 and TLR4 activation. The proposed reporter-cell assay uses cultured HEK293 cells that have been transfected with a chimeric protein consisting of the extracellular portion of the TLR2 or TLR4 receptor, conjugated with a truncated placental alkaline phosphatase enzyme. Ligand binding to the receptor initiates the production of a colored metabolite which can be quantified in a spectrophotometer.

Exploratory Outcome: Lipidomics

As an additional component of the biological signature of XN in CD, lipidomic analysis will be performed by UPLC-QTOF. These data will be combined with the results of XN metabolite and bile acid profiles in modeling the biological signature.

13 Participant timeline:

Table 2							
	Phone Screening	Clinical Screening	Baseline Clinical Visit - Week 0	Randomization Visit – within 48hrs after Baseline	Bi-weekly Clinical Visits (Weeks 2,6)	Midpoint Clinical Visit- Week 4	Trial Closeout- Week 8
Oral waiver of consent	Х						
Initial eligibility screening	Х						
Written informed consent		X	Х				
W9 Form		Х					
Written release of medical records				X			
Demographics		Х					
Randomization				Х			
Assessment of Symptoms/AEs			Х		Х	Х	X
PROMIS-29			Х		Х	Х	Х
Disease Activity scale (CDAI)	Х	Х	Х		Х	Х	X

Protocol

	KESEAR		IUIE		Template Version	n 02.02.17
Adherence assessment (verbal recall)				Х	Х	Х
Adherence						
assessment					Х	Х
(pill count)						
Labs: CBC, &						
Toxicology	Х	Х		Х	Х	Х
Panel (Chem 13), CRP	71	7		1	7	~~~~~~~~~~~~~~~~~~~~~~~~~~~~~~~~~~~~~~~
Blood collection	Х	Х		Х	Х	Х
Urine collection			Х	Х	Х	Х
Stool collection			Х	Х	Х	Х
XN or placebo dispensed			Х		Х	
Stipend ordered					Х	Х
Participant Discharged						Х

13b Missed visits

In the case of an inability to conduct study visits as intended the study team will move forward with the following procedures according to the circumstantial requirements.

1. Participants refuse or are unable to come in for a Week 2 or Week 6 (Interim) visit: Study Procedures:

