A Data Safety and Monitoring Board (DSMB) independent of the study team will be created for the proposed trial and will consist of: a clinical investigator with IBD experience, a clinician with IBD practice experience, a biostatistician, and at least one other experienced clinical researcher/trialist. The DSMP will review all AE reports according to IRB policy, monthly reports of recruitment, retention and overall study progress; and attend quarterly meetings. Protocol amendments can be suggested by members of the independent monitoring committee at any time, and additional meetings of the DSMB can be called by any member at any time. The PI and study coordinator will also participate in quarterly meetings with the committee to provide additional information and/or clarify reports.

21b This study will be stopped prior to its completion if the intervention is associated with adverse effects that call into question the safety of the intervention, if any new information becomes

Protocol

available during the trial that necessitates stopping the trial; or if other situations occur that might warrant stopping the trial. The ultimate decision to stop the trial may be made by the DSMB, NCCIH, and/or the FDA.

The trial will be halted if >25% of the total sample experience moderate or greater AEs or laboratory abnormalities requiring them to withdraw.

The DSMB will provide a final recommendation to the PI to halt the study or amend the study protocol, and will develop a response plan, in consultation with the NUNM IRB and the NCCIH Program Officer.

If immediate changes are required for participant safety, enrollment and other study activities will not continue until the modifications/amendment is approved by the IRB.

22 Harms

Adverse Event Monitoring and Reporting

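### Read plainly, the only numeric halting limit in section 21b leaves out qualifying laboratory values first found at the Week 8 closeout visit

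*Protocol*

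**What the plan says.** Section 21b of the protocol has two kinds of stop. One is a matter of judgement: the study stops early "if the intervention is associated with adverse effects that call into question the safety of the intervention", or on new information or other circumstances that warrant it. The other is the only one with a number: "The trial will be halted if >25% of the total sample experience moderate or greater AEs or laboratory abnormalities requiring them to withdraw".

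Withdrawal of an individual is governed by section 11b. Besides new, moderately severe gastrointestinal events attributed to the intervention, it covers laboratory results: "Participants will also be withdrawn if they have any" critical value on the routine safety tests. No time limit is attached.

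The schedule comes from sections 8, 12 and 13. Study product is "taken by mouth once daily for 8 weeks". On safety testing, section 12 says: "Standard clinical Complete Blood Counts and toxicology panels including liver and renal function tests will be measured at each bi-weekly clinical visit". Table 2 places these tests and the AE assessment at Weeks 2, 4, 6 and 8. The row "Participant Discharged" is marked only at Trial Closeout, Week 8.

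Section 12 adds that abnormal values meeting halting criteria are recorded in the database. It does not define those criteria there or link them to the 25% limit.

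On the Phase 1 trial, section 6a reports: "At Closeout/Week 8, 2 laboratory parameters met halting criteria in Group B, including 1 mild anemia and 1 AST elevation".

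**The concern.** The numerator of the limit depends on a consequence (withdrawal) and not on the event itself. At Week 8 that consequence is no longer available in any ordinary sense: dosing is finished, the participant is discharged, and laboratory results come back after the draw. One of the four post-baseline safety checks, the one after the longest exposure, therefore seems to fall outside the count. The primary outcome is labelled as cumulative toxicology, so this is the visit where a cumulative effect would be furthest advanced.

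What is at stake is the reliability of the one trigger in 21b that works from a count. Where participants enter over time, a pattern seen at Week 8 in those who finish early would add nothing to the count that could halt the trial for those still to be treated. Any protection would then have to come from the discretionary stop.

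A related difficulty is that sections 11b, 12 and 21b use three different terms for a serious laboratory finding (a critical value, a value meeting halting criteria, and an abnormality that makes withdrawal necessary) without saying how they relate.

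**Working it through.** **The text, side by side**

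| Element | Where | Content |
|---|---|---|
| Numeric limit | 21b | More than 25% of the total sample, counted through withdrawal |
| Individual laboratory withdrawal | 11b | A critical value; no timing stated |
| Values meeting halting criteria | 12 | Recorded; not defined; no link to 21b |
| Safety tests | 12, Table 2 | Weeks 2, 4, 6 and 8 after baseline |
| End of dosing | 8, 11a | After 8 weeks |
| Discharge | Table 2 | Week 8 only |

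For a laboratory value, the withdrawal condition applies however the sentence in 21b is parsed. For AEs, it applies only if the closing phrase of that sentence also modifies AEs, which the grammar leaves open.

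**The limit as a count**

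The protocol gives the limit only as a percentage, with no count and no operating characteristics, so there is no figure of its own to reproduce. Section 6a states "We will recruit 32 participants with CD". With N = 32, 25% is 8, so more than 25% means at least 9 (9/32 = 28.1%). If the total were read as the 24 expected to complete, it would mean at least 7 (7/24 = 29.2%).

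**Illustration 1: a share of events first seen at Week 8**

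Let p be the true proportion of all participants, both arms together, with a qualifying event, and s the share of those events first seen at Week 8. Both are assumptions. The proportion that counts is p(1 − s), and the chance of meeting the limit by trial end is P(X ≥ 9) with X ~ Binomial(32, p(1 − s)). The value s = 0.25 is an equal share over four checks.

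| p | Week 8 counted (s = 0) | s = 0.25: counted proportion | s = 0.25: chance | s = 0.50: chance |
|---|---|---|---|---|
| 10% | 0.003 | 7.5% | <0.001 | <0.001 |
| 15% | 0.041 | 11.25% | 0.007 | <0.001 |
| 20% | 0.17 | 15% | 0.041 | 0.003 |
| 30% | 0.66 | 22.5% | 0.28 | 0.041 |
| 35% | 0.84 | 26.25% | 0.47 | 0.093 |

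**Illustration 2: a constant rate per draw**

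Let q be the assumed chance of a qualifying value at each draw. The counted proportion is 1 − (1 − q)^k, with k = 4 if Week 8 counts and k = 3 if it does not.

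| q | k = 4: proportion, chance | k = 3: proportion, chance |
|---|---|---|
| 0.05 | 0.185, 0.12 | 0.143, 0.03 |
| 0.08 | 0.284, 0.58 | 0.221, 0.26 |
| 0.10 | 0.344, 0.82 | 0.271, 0.51 |
| 0.15 | 0.478, 0.99 | 0.386, 0.92 |

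Both models point the same way. The loss is large when the true proportion is near the limit, and small when it is far below or far above it.

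**The case against.** Four points can fairly be made in the plan's defence.

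*The exclusion of Week 8 is inferred.* A reader might conclude that a Week 8 value can never count. The protocol does not say so. The withdrawal rule in 11b has no time limit, 21b does not exclude any visit, and a DSMB could treat the withdrawal phrase as a standard of severity, counting a value that would have led to withdrawal had dosing continued. This stands. What remains is that the plain wording points one way and a lenient reading the other, in the only numeric limit the trial has.

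*Week 8 events are not lost to safety oversight.* A clinical investigator reviews all laboratory results (section 12). The DSMB reviews safety reports quarterly, can recommend termination, and any member can call an extra meeting (sections 21a and 22). The discretionary stop has no withdrawal condition. This also stands, and it confines the gap to the numeric limit. It does not remove it, because a numeric limit is there to act without a judgement call.

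*Phase 1 does not show harm from such a rule.* A reader might infer that the two Phase 1 values would have been missed by the Phase 2 limit because of their timing. The documents do not support that. The anemia was mild, all Week 8 abnormalities resolved on re-testing, there were no severe or serious AEs, and nobody discontinued because of AEs. Nothing shows that either value would have required withdrawal at any visit, and section 6a does not say whether earlier visits had similar values. Phase 1 shows only that values meeting its halting criteria can occur at that visit.

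*The limit may seldom matter.* The protocol anticipates very few discontinuations for adverse effects. At true rates of 10% to 15% the limit is almost never met even with Week 8 counted (0.003 and 0.041). This stands as a bound on the practical effect.

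**Conclusion.** The point holds in limited form. As plainly worded, the numeric limit in 21b leaves out a qualifying laboratory value first found at the closeout visit, and also AEs first reported there if the withdrawal phrase covers AEs. The wording allows a second reading, and the other safeguards remain in force for Week 8 events.

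The size cannot be fixed from the documents. If a quarter of qualifying events first appear at Week 8, the chance of meeting the limit drops by 0.37 at a true rate of 30% (0.656 − 0.282 = 0.374) and by 0.13 at 20% (0.175 − 0.041 = 0.134). At 10% the difference is negligible. These figures assume a total sample of 32, independent participants, and event rates and a Week 8 share that the protocol does not state. They also describe the position at trial end, so they are not the chance of halting early enough to spare later participants.

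Priority is minor to moderate: a cheap improvement to the wording of a safety rule, with no evidence that anyone would be harmed under the present text.

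**What to change.** Reconcile section 21b with section 11b, with the halting criteria mentioned in section 12, and with Table 2. State in 21b that the numerator is the number of participants whose AE or laboratory value meets the withdrawal criterion that the sponsor and DSMB choose to keep, at any scheduled safety assessment including Week 8, whether or not the participant can still be withdrawn. State also whether the condition applies to AEs as well as to laboratory values, and how the three terms in 11b, 12 and 21b relate.

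The 25% limit and the individual withdrawal criteria are left to the sponsor and DSMB; nothing here requires changing either.

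The cost is a sentence or two in 21b, matching terms in 11b and 12, and one added count in the DSMB report. The Week 8 tests and AE assessment are already scheduled, so no new data are needed. The one downside is that the limit may be met somewhat more often.
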